### 12.2 Disease Parameters

**Measurable disease:** Measurable lesions are defined as those that can be accurately measured in at least one dimension (longest diameter to be recorded) as >20 mm by chest x-ray, as >10 mm with CT scan, or >10 mm with calipers by clinical exam. All tumor measurements must be recorded in millimeters (or decimal fractions of centimeters).

**Malignant lymph nodes:** To be considered pathologically enlarged and measurable, a

lymph node must be  $>15$  mm in short axis when assessed by CT scan (CT scan slice thickness recommended to be no greater than 5 mm). At baseline and in follow-up, only the short axis will be measured and followed.

**Non-measurable disease:** All other lesions (or sites of disease), including small lesions (longest diameter  $<10$  mm or pathological lymph nodes with  $\geq 10$  to  $<15$  mm short axis), are considered non-measurable disease. Bone lesions, leptomeningeal disease, ascites, pleural/pericardial effusions, lymphangitis cutis/pulmonitis, inflammatory breast disease, and abdominal masses (not followed by CT or MRI), are considered as non-measurable.

*Note: Cystic lesions that meet the criteria for radiographically defined simple cysts should not be considered as malignant lesions (neither measurable nor non-measurable) since they are, by definition, simple cysts.*

‘Cystic lesions’ thought to represent cystic metastases can be considered as measurable lesions, if they meet the definition of measurability described above. However, if non-cystic lesions are present in the same patient, these are preferred for selection as target lesions.

**Target lesions:** All measurable lesions up to a maximum of 2 lesions per organ and 5 lesions in total, representative of all involved organs, should be identified as target lesions and recorded and measured at baseline. Target lesions should be selected on the basis of their size (lesions with the longest diameter), be representative of all involved organs, but in addition should be those that lend themselves to reproducible repeated measurements. It may be the case that, on occasion, the largest lesion does not lend itself to reproducible measurement in which circumstance the next largest lesion which can be measured reproducibly should be selected. A sum of the diameters (longest for non-nodal lesions, short axis for nodal lesions) for all target lesions will be calculated and reported as the baseline sum diameters. If lymph nodes are to be included in the sum, then only the short axis is added into the sum. The baseline sum diameters will be used as reference to further characterize any objective tumor regression in the measurable dimension of the disease.

**Non-target lesions:** All other lesions (or sites of disease) including any measurable lesions over and above the 5 target lesions should be identified as non-target lesions and should also be recorded at baseline. Measurements of these lesions are not required, but the presence, absence, or in rare cases unequivocal progression of each should be noted throughout follow-up.

### 12.3 Methods for Evaluation of Measurable Disease

All measurements should be taken and recorded in metric notation using a ruler or calipers. All baseline evaluations should be performed as closely as possible to the beginning of treatment and never more than 4 weeks before the beginning of the treatment.

The same method of assessment and the same technique should be used to characterize each identified and reported lesion at baseline and during follow-up. Imaging-based

evaluation is preferred to evaluation by clinical examination unless the lesion(s) being followed cannot be imaged but are assessable by clinical exam.

**Clinical lesions:** Clinical lesions will only be considered measurable when they are superficial (e.g., skin nodules and palpable lymph nodes) and  $\geq 10$  mm diameter as assessed using calipers (e.g., skin nodules). In the case of skin lesions, documentation by color photography, including a ruler to estimate the size of the lesion, is recommended.

**Chest x-ray:** Lesions on chest x-ray are acceptable as measurable lesions when they are clearly defined and surrounded by aerated lung. However, CT is preferable.

**Conventional CT and MRI:** This guideline has defined measurability of lesions on CT scan based on the assumption that CT slice thickness is 5 mm or less. If CT scans have slice thickness greater than 5 mm, the minimum size for a measurable lesion should be twice the slice thickness. MRI is also acceptable in certain situations (e.g. for body scans).

Use of MRI remains a complex issue. MRI has excellent contrast, spatial, and temporal resolution; however, there are many image acquisition variables involved in MRI, which greatly impact image quality, lesion conspicuity, and measurement. Furthermore, the availability of MRI is variable globally. As with CT, if an MRI is performed, the technical specifications of the scanning sequences used should be optimized for the evaluation of the type and site of disease. Furthermore, as with CT, the modality used at follow-up should be the same as was used at baseline and the lesions should be measured/assessed on the same pulse sequence. It is beyond the scope of the RECIST guidelines to prescribe specific MRI pulse sequence parameters for all scanners, body parts, and diseases. Ideally, the same type of scanner should be used and the image acquisition protocol should be followed as closely as possible to prior scans. Body scans should be performed with breath-hold scanning techniques, if possible.

**PET-CT:** At present, the low dose or attenuation correction CT portion of a combined PET-CT is not always of optimal diagnostic CT quality for use with RECIST measurements. However, if the site can document that the CT performed as part of a PET-CT is of identical diagnostic quality to a diagnostic CT (with IV and oral contrast), then the CT portion of the PET-CT can be used for RECIST measurements and can be used interchangeably with conventional CT in accurately measuring cancer lesions over time. Note, however, that the PET portion of the CT introduces additional data which may bias an investigator if it is not routinely or serially performed.

**Ultrasound:** Ultrasound is not useful in assessment of lesion size and should not be used as a method of measurement. Ultrasound examinations cannot be reproduced in their entirety for independent review at a later date and, because they are operator dependent, it cannot be guaranteed that the same technique and measurements will be taken from one assessment to the next. If new lesions are identified by ultrasound in the course of the study, confirmation by CT or MRI is advised. If there is concern about radiation exposure at CT, MRI may be used instead of CT in selected instances.

**Endoscopy, Laparoscopy:** The utilization of these techniques for objective tumor evaluation is not advised. However, such techniques may be useful to confirm complete pathological response when biopsies are obtained or to determine relapse in trials where recurrence following complete response (CR) or surgical resection is an endpoint.

**Tumor markers:** Tumor markers alone cannot be used to assess response. If markers are initially above the upper normal limit, they must normalize for a patient to be considered in complete clinical response. Specific guidelines for both CA-125 response (in recurrent ovarian cancer) and PSA response (in recurrent prostate cancer) have been published [JNCI 96:487-488, 2004; J Clin Oncol 17, 3461-3467, 1999; J Clin Oncol 26:1148-1159, 2008]. In addition, the Gynecologic Cancer Intergroup has developed CA-125 progression criteria which are to be integrated with objective tumor assessment for use in first-line trials in ovarian cancer [JNCI 92:1534-1535, 2000].

**Cytology, Histology:** These techniques can be used to differentiate between partial responses (PR) and complete responses (CR) in rare cases (e.g., residual lesions in tumor types, such as germ cell tumors, where known residual benign tumors can remain).

The cytological confirmation of the neoplastic origin of any effusion that appears or worsens during treatment when the measurable tumor has met criteria for response or stable disease is mandatory to differentiate between response or stable disease (an effusion may be a side effect of the treatment) and progressive disease.

**FDG-PET:** While FDG-PET response assessments need additional study, it is sometimes reasonable to incorporate the use of FDG-PET scanning to complement CT scanning in assessment of progression (particularly possible 'new' disease). New lesions on the basis of FDG-PET imaging can be identified according to the following algorithm:

- Negative FDG-PET at baseline, with a positive FDG-PET at follow-up is a sign of PD based on a new lesion.
- No FDG-PET at baseline and a positive FDG-PET at follow-up: If the positive FDG-PET at follow-up corresponds to a new site of disease confirmed by CT, this is PD. If the positive FDG-PET at follow-up is not confirmed as a new site of disease on CT, additional follow-up CT scans are needed to determine if there is truly progression occurring at that site (if so, the date of PD will be the date of the initial abnormal FDG-PET scan). If the positive FDG-PET at follow-up corresponds to a pre-existing site of disease on CT that is not progressing on the basis of the anatomic images, this is not PD.
- FDG-PET may be used to upgrade a response to a CR in a manner similar to a biopsy in cases where a residual radiographic abnormality is thought to represent fibrosis or scarring. The use of FDG-PET in this circumstance should be prospectively described in the protocol and supported by disease-specific medical literature for the indication. However, it must be acknowledged that both approaches may lead to false positive CR due to limitations of FDG-PET and biopsy resolution/sensitivity.

*Note: A ‘positive’ FDG-PET scan lesion means one which is FDG avid with an uptake greater than twice that of the surrounding tissue on the attenuation corrected image.*

## 12.4 Response Criteria

### 12.4.1 Evaluation of Target Lesions

**Complete Response (CR):** Disappearance of all target lesions. Any pathological lymph nodes (whether target or non-target) must have reduction in short axis to <10 mm.

**Partial Response (PR):** At least a 30% decrease in the sum of the diameters of target lesions, taking as reference the baseline sum diameters.

**Progressive Disease (PD):** At least a 20% increase in the sum of the diameters of target lesions, taking as reference the smallest sum on study (this includes the baseline sum if that is the smallest on study). In addition to the relative increase of 20%, the sum must also demonstrate an absolute increase of at least 5 mm. (Note: the appearance of one or more new lesions is also considered progressions).

**Stable Disease (SD):** Neither sufficient shrinkage to qualify for PR nor sufficient increase to qualify for PD, taking as reference the smallest sum diameters while on study.

### 12.4.2 Evaluation of Non-Target Lesions

**Complete Response (CR):** Disappearance of all non-target lesions and normalization of tumor marker level. All lymph nodes must be non-pathological in size (<10 mm short axis).

*Note: If tumor markers are initially above the upper normal limit, they must normalize for a patient to be considered in complete clinical response.*

**Non-CR/Non-PD:** Persistence of one or more non-target lesion(s) and/or maintenance of tumor marker level above the normal limits.

**Progressive Disease (PD):** Appearance of one or more new lesions and/or unequivocal progression of existing non-target lesions. Unequivocal progression should not normally trump target lesion status. It must be representative of overall disease status change, not a single lesion increase.

Although a clear progression of “non-target” lesions only is exceptional, the opinion of the treating physician should prevail in such circumstances, and the progression status should be confirmed at a later time by the review panel (or Principal Investigator).

### 12.4.3 Evaluation of Best Overall Response

The best overall response is the best response recorded from the start of the treatment until disease progression/recurrence (taking as reference for progressive disease the smallest measurements recorded since the treatment started). The patient's best response assignment will depend on the achievement of both measurement and confirmation criteria.

#### For Patients with Measurable Disease (i.e., Target Disease)

Target Lesions	Non-Target Lesions	New Lesions	Overall Response	Best Overall Response when Confirmation is Required*
CR	CR	No	CR	>4 wks. Confirmation**
CR	Non-CR/Non-PD	No	PR	>4 wks. Confirmation**
CR	Not evaluated	No	PR	
PR	Non-CR/Non-PD/not evaluated	No	PR	
SD	Non-CR/Non-PD/not evaluated	No	SD	Documented at least once >4 wks. from baseline**
PD	Any	Yes or No	PD	no prior SD, PR or CR
Any	PD***	Yes or No	PD	
Any	Any	Yes	PD	

\* See RECIST 1.1 manuscript for further details on what is evidence of a new lesion.  
 \*\* Only for non-randomized trials with response as primary endpoint.  
 \*\*\* In exceptional circumstances, unequivocal progression in non-target lesions may be accepted as disease progression.  
 Note: Patients with a global deterioration of health status requiring discontinuation of treatment without objective evidence of disease progression at that time should be reported as "symptomatic deterioration." Every effort should be made to document the objective progression even after discontinuation of treatment.

#### For Patients with Non-Measurable Disease (i.e., Non-Target Disease)

Non-Target Lesions	New Lesions	Overall Response
CR	No	CR
Non-CR/non-PD	No	Non-CR/non-PD*
Not all evaluated	No	not evaluated
Unequivocal PD	Yes or No	PD
Any	Yes	PD

\* 'Non-CR/non-PD' is preferred over 'stable disease' for non-target disease since SD is increasingly used as an endpoint for assessment of efficacy in some trials so to assign this category when no lesions can be measured is not advised

#### **12.4.4 Duration of Response**

**Duration of overall response:** The duration of overall response is measured from the time measurement criteria are met for CR or PR (whichever is first recorded) until the first date that recurrent or progressive disease is objectively documented (taking as reference for progressive disease the smallest measurements recorded since the treatment started).

The duration of overall CR is measured from the time measurement criteria are first met for CR until the first date that progressive disease is objectively documented.

**Duration of stable disease:** Stable disease is measured from the start of the treatment until the criteria for progression are met, taking as reference the smallest measurements recorded since the treatment started, including the baseline measurements.

#### **12.4.5 Progression-Free Survival**

PFS is defined as the duration of time from start of treatment to time of progression or death, whichever occurs first.

#### **12.4.6 Response Review**

It is strongly recommended that all responses be reviewed by an expert(s) independent of the study at the study's completion.

### **13.0 DATA AND SAFETY MONITORING**

In compliance with the Washington University Institutional Data and Safety Monitoring Plan, the Principal Investigator will provide a Data and Safety Monitoring (DSM) report to the Washington University Quality Assurance and Safety Monitoring Committee (QASMC) semi-annually beginning six months after accrual has opened (if at least five patients have been enrolled) or one year after accrual has opened (if fewer than five patients have been enrolled at the six-month mark).

The Principal Investigator will review all patient data at least every six months, and provide a semi-annual report to the QASMC. This report will include:

- HRPO protocol number, protocol title, Principal Investigator name, data coordinator name, regulatory coordinator name, and statistician
- Date of initial HRPO approval, date of most recent consent HRPO approval/revision, date of HRPO expiration, date of most recent QA audit, study status, and phase of study
- History of study including summary of substantive amendments; summary of accrual suspensions including start/stop dates and reason; and summary of protocol exceptions, error, or breach of confidentiality including start/stop dates and reason
- Study-wide target accrual and study-wide actual accrual

- Protocol activation date
- Average rate of accrual observed in year 1, year 2, and subsequent years
- Expected accrual end date and accrual by cohort
- Objectives of protocol with supporting data and list the number of participants who have met each objective
- Measures of efficacy
- Early stopping rules with supporting data and list the number of participants who have met the early stopping rules
- Summary of toxicities separated by cohorts
- Abstract submissions/publications
- Summary of any recent literature that may affect the safety or ethics of the study

The study principal investigator and Research Patient Coordinator will monitor for serious toxicities on an ongoing basis. Once the principal investigator or Research Patient Coordinator becomes aware of an adverse event, the AE will be reported to the HRPO and QASMC according to institutional guidelines. All adverse events are tracked in the OnCore database.

## **14.0 STATISTICAL CONSIDERATIONS**

### **14.1 Study Design**

This is a two cohort, open label, nonrandomized study with a noninferiority primary endpoint. The last ten patients enrolled after accrual to the dextrazoxane treatment group has been completed will be considered a control group; the purpose of this group is to obtain control samples for some of the correlative studies. The primary endpoint will be tested only in the active treatment cohort. Toxicity and cardiac function biomarkers will be documented in both cohorts.

### **14.2 Primary Endpoint**

We are comparing the progression-free survival (PFS) rate of patients being treated with doxorubicin in combination with dextrazoxane to a historic control established by Judson et al in 2014. PFS is defined as the time from randomization to the first occurrence of progression or death due to any cause. If no event exists, the PFS will be censored at the last scheduled disease assessment on study. Patients who have reached their maximum follow-up and have remained progression-free will be censored for progression at the date of their last disease assessment. Intention to treat principles will be used for analyzing the primary endpoint. The primary endpoint will be tested using estimates of median PFS and 95% confidence intervals derived from Kaplan-Meier models.

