### **14.3.1 Sample Size and Statistical Power**

The historic control used for comparison is based on data published by Judson et al. Patients with advanced or metastatic soft tissue sarcoma treated with single agent doxorubicin had a median PFS of 4.6 months. We consider a median PFS of 3.7 months (safety margin of 20%) to be non-inferior to the PFS seen in patients treated with doxorubicin alone. We will be using a one-sided log-rank test at an alpha level of 0.05 with a power of 0.80 to determine if treatment of doxorubicin with upfront dextrazoxane is non-inferior to doxorubicin alone.

[figure not shown]
A maximum of 65 patients may be enrolled to allow for a 10% dropout rate, resulting in at least 57 patients for testing of the primary endpoint. Using 57 patients, we have 0.80 power at a 1-sided significance level of 0.05 to detect a median PFS 3.7 months compared to this historic control's PFS of 4.6 months.

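### Sections 14.2 and 14.3.1 each name a different deciding analysis of the primary endpoint, and no readable text says which one settles non-inferiority

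*Combined protocol and SAP*

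**What the plan says.** Section 14.1 sets the frame: "This is a two cohort, open label, nonrandomized study with a noninferiority primary endpoint", and "The primary endpoint will be tested only in the active treatment cohort". The comparison is therefore one cohort against a historic median of 4.6 months.

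Section 14.2, headed Primary Endpoint, gives one analysis sentence: "The primary endpoint will be tested using estimates of median PFS and 95% confidence intervals derived from Kaplan-Meier models". It does not say whether the interval is one- or two-sided, which limit is used, or what value that limit must exceed.

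Section 14.3.1 gives another: "We will be using a one-sided log-rank test at an alpha level of 0.05 with a power of 0.80" and, continuing, "to determine if treatment of doxorubicin with upfront dextrazoxane is non-inferior to doxorubicin alone". It also sets the margin, "We consider a median PFS of 3.7 months (safety margin of 20%) to be non-inferior". It then closes with a power statement for 57 patients in which the trial is able "to detect a median PFS 3.7 months compared to this historic" control's 4.6 months. A figure follows the log-rank sentence and is not shown in the text available to us.

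On the time origin, section 14.2 says "PFS is defined as the time from randomization to the first occurrence of progression or death due to any cause", while section 12.4.5 counts from the start of treatment.

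**The concern.** Both sentences are confirmatory. One says the endpoint is tested by an interval for the median; the other says a log-rank test determines non-inferiority. They are different procedures. The interval for the median depends on how many events fall before one time point, whereas the log-rank test uses the whole curve. They can give different answers on the same data, and the readable text does not say which prevails.

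The levels may differ too. If the 95% interval is two-sided, which is the usual reading but is not stated, its lower limit works at one-sided 0.025 against the 0.05 of section 14.3.1.

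The role of 3.7 months is also unclear. One sentence makes it the non-inferiority margin, which belongs at the null boundary. The power sentence makes it the value to be detected against 4.6, which belongs in the alternative.

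At stake is the single headline conclusion of an open-label trial: with the rule left open, the same data could be reported as non-inferior or not.

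**Working it through.** **Inputs.** From 14.3.1: historic median 4.6 months, margin 3.7 months (3.7/4.6 = 0.804, a 19.6% reduction), 57 patients, one-sided alpha 0.05, power 0.80. From 12.1 and the study calendar: disease assessment every 6 weeks. Our assumptions: 3.7 is the null boundary; all 57 patients have an event; the log-rank test is the one-sample form against a reference curve with median 3.7; the Kaplan-Meier (KM) rule is that the lower two-sided 95% limit exceeds 3.7. The plan states none of these four.

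**Step 1: the plan's own power.** ln(4.6/3.7) = 0.2177. With exponential PFS and continuous times, power = Φ(√57 × 0.2177 − 1.645) = Φ(1.644 − 1.645) = 0.50. An exact gamma calculation gives 0.52, and simulation gives 0.48 to 0.52 depending on the variance form. The stated 0.80 is not reproduced; on this formula it needs (2.487/0.2177)² ≈ 131 events. With a Weibull curve the log hazard ratio is multiplied by the shape, so 0.80 is reached at a shape of 2.487/(√57 × 0.2177) = 1.51.

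**Step 2: the KM rule.** With 57 uncensored times the lower 95% limit is the 22nd event time (plain or log transform) or the 21st (log-log). The rule passes if at most 21 or 20 events occur by 3.7 months. At a true median of 4.6, the chance of an event by then is 1 − 2^(−3.7/4.6) = 0.427, and the Binomial(57, 0.427) probability is 0.22 or 0.15. At a true 3.7 it is 0.03 or 0.02.

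**Step 3: the two rules on the same simulated data.** KM ranges cover the log and log-log limits.

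| Scenario | Log-rank passes | KM rule passes | Disagree |
|---|---|---|---|
| True 4.6, exponential, continuous times | 0.48 | 0.15–0.22 | 0.33–0.37 |
| True 4.6, Weibull shape 1.51, continuous times | 0.78 | 0.31–0.41 | 0.41–0.50 |
| Underlying 4.6, exponential, 6-weekly scans | 0.79 | 0.63–0.73 | 0.23–0.28 |

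In the third row each progression is recorded at the next scan (6 weeks ≈ 1.38 months), which pushes recorded times later and so raises both pass rates. If the underlying median is lowered by half a scan interval (4.6 − 0.69 = 3.91), the log-rank test passes in 0.34 and the KM rule in 0.34 to 0.45, so the KM rule is no longer the weaker one.

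**Step 4: choosing the rule afterwards.** At a true 3.7 with continuous times, at least one rule passes in 0.05 to 0.06 of trials, against 0.04 for the log-rank test alone. With an underlying 3.7 and 6-weekly recording, the log-rank test alone passes in 0.20 and at least one rule in 0.33 to 0.40.

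**Step 5: does it rest on the 0.025 reading?** No. If the 95% limit is read as one-sided, matching alpha 0.05, the rules still disagree in 0.30 to 0.33 of trials at 4.6 (exponential, continuous times).

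**The case against.** The strongest reply is that the sections can be reconciled. Section 14.3.1 gives a test, side, level, margin and purpose; section 14.2 would then list what is to be estimated and reported, with its verb loosely chosen. That is a plausible reading, and the fix below adopts it. But section 14.2 is the section on the primary endpoint, its only analysis sentence is worded as a test, and nothing readable subordinates it to 14.3.1. The reader has to supply the link.

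A second reply is that the disagreement rates compare two rules the plan never fully states. This stands. Section 14.2 has no pass criterion and 14.3.1 names no reference curve or variance form, so the rates are illustrations.

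A third is that continuous event times do not match 6-weekly scans. This also stands, and it matters: it changes which rule is stronger and how much a late choice costs. It does not remove the disagreement.

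Four stronger readings are tempting, and the documents do not support them:
- That the plan states no hypotheses. The figure not shown in 14.3.1 may contain them.
- That the two levels certainly differ. The sidedness of the interval is not given.
- That the true power is 0.50. This holds under exponential PFS, 57 events and continuous times; the figure may hold another reference distribution, and a Weibull shape near 1.5 gives about 0.80.
- That picking the rule afterwards inflates error only slightly, or a great deal. Either can be shown, depending on how progression is recorded.

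**Conclusion.** The conflict is real and is visible in the text without any simulation: two confirmatory analyses of one primary endpoint, no link between them, and no readable statement of which decides. The readable text also puts 3.7 months in two incompatible roles; whether the missing figure settles this cannot be checked.

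Under the assumptions listed, the rules would disagree in roughly a quarter to a half of trials at a true median of 4.6 months (0.23 to 0.50 across the three scenarios). The existence of material disagreement is robust to the distribution, the interval transform, the sidedness of the interval and the scan schedule. Its exact size is not, nor is the ranking of the two rules by power. The gap between 0.50 and the stated 0.80 is conditional and calls for an explanation of the power calculation; it does not establish that the trial is underpowered.

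**What to change.** Replace the last sentence of 14.2 with one deciding rule and repeat it in 14.3.1. For example:

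> H0: the PFS curve is no better than [named reference curve with median 3.7 months]. H1: it is better. H0 is tested by a one-sample log-rank test at one-sided alpha 0.05. Non-inferiority is declared only if H0 is rejected. The Kaplan-Meier median and its confidence interval are reported as supporting description and do not decide.

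The hypothesis concerns the curve because the log-rank test compares whole curves. The reference curve must be named, and should refer to progression times recorded as they will be in this trial. Keeping the Kaplan-Meier interval as the deciding rule would also end the ambiguity, provided its limit, threshold and level are stated.

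Then:
- Check the hypotheses against the figure in 14.3.1 and align them.
- Reword the power sentence to the same hypotheses. Either state the reference distribution and assumptions that give 0.80 with 57 patients, or restate the power (about 0.50 at a true median of 4.6 under exponential PFS, 57 events and continuous times).
- Minor: in 14.2, start PFS at the start of treatment, as in 12.4.5, since the study is not randomized.

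Cost: wording in two sections, plus the work of choosing and justifying the reference curve. No extra patients, visits or data. The possible downside is a less favourable stated power.
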